4.1.2.2 Part II: Multiple-Ascending Dose-Escalation (Multiple Participant Cohorts)

A modified continual reassessment method with overdose control (mCRM-EWOC) will guide the dose-escalation to determine the MTD, by using primary safety variables (e.g., DLT). This model-based design assigns participants to dose-levels and defines the MTD based on the estimation of the target toxicity level by a model depicting the dose-toxicity relationship. The dose-toxicity relationship is described by a two-parameter logistic regression model, which is continuously updated as additional participant information becomes available.

The prior distribution for the parameters of the DLT dose-response curve will be a mixture of informative and minimally informative components. The minimally informative component makes the design robust against unforeseen deviations from the informative component and will be constructed based on the assumed not toxic and toxic doses. For the dose toxicity relationship of the minimally informative component, it is conservatively assumed that it would be very unlikely that 10% or higher DLT rates are associated with the first dose of the monotherapy dose-escalation and that it would be very unlikely that a 25% or lower DLT rate is associated with a dose of 400 mg (additional details provided in [Appendix 8](#)). The informative component will be the posterior distribution of the CEA TCB (*cibisatamab*) monotherapy toxicity data without obinutuzumab pre-treatment, as of cutoff date 20 July 2017, approximated with a bivariate normal distribution. The two components will be mixed in a 10/90% ratio (informative prior component 10%; minimally informative component 90%). Further details are provided in [Appendix 8](#).

The MTD is defined as the dose with the highest probability that the DLT rate is within the target of 20% to 35%, and a relatively low probability (< 25%) that the DLT rate is above 35%.

- Dose-escalation to IV MTD

The Part II dose-escalation will start with a dose of 1.6 mg (flat dose) IV Q3W (Section 4.3 Dose Justification) if this dose has been reached in Part I and considered safe. In the eventuality that Part I has been stopped because of the occurrence of a RO7172508-related Grade ≥ 2 AE (or DLT) then, the starting-dose of Part II will not exceed the dose-level at which the AE that delineated the end of Part I occurred. Furthermore, the grade and type of AE will also be considered, when choosing the dose-level for Part II. In the eventuality that the Sponsor decides to initiate Part II in the absence of an observed RO7172508-related Grade ≥ 2 toxicity and prior to the dose-level reaching 1.6 mg, then the starting-dose of Part II will not exceed the highest dose tested in Part I. If the starting-dose of Part II is the same as the last dose in Part I, the participant treated at the last dose in Part I could be considered as the first participant of the cohort for Part II. If the initial dose is not tolerated, then participants for the subsequent cohort may be enrolled at a lower RO7172508 dose than the initially selected Part II starting-dose. The maximum dose of RO7172508 will be 400 mg (flat dose IV). The initial dosing regimen in Part II may also be adapted depending on emerging data in Part I.

In Part II dose-escalation, a minimum of 3 participants per cohort *will be enrolled who have a baseline sCEA level ≤ 20 ng/ml*. Participants within a cohort will be treated in a sequential manner with one week between the first and second participant, and at least one day between subsequent participants. However, if the first participant experiences a DLT within the first 7 days, then the time between the treatment of subsequent participants within the same cohort may be increased. The DLT evaluation window in Part II is defined as a period of 3 weeks after the first administration of RO7172508 in an IV Q3W schedule. Based on emerging data, the interval between dosing of each participant within a cohort or the DLT window may be adjusted if deemed appropriate by the Investigators and/or the Sponsor.

For each cohort, all participants will be followed through a 3-week DLT window (i.e., 21 days *after the first dose of RO7172508*). If fractionated dosing is implemented in Cycle 1 to improve tolerability, the DLT window will be extended to include the cycle where the planned target dose is administered in full i.e., *Cycle 1 Day 1 until the end of Cycle 2*. The DLT window will therefore be 6 weeks (42 days), or 8 weeks (56 days) if treatment has been delayed for no more than 14 days.

A new cohort can be opened when at least 3 evaluable participants of the previous cohort have completed the DLT window. *At least 3 evaluable participants must have a baseline sCEA level of ≤ 20 ng/ml.* If participants experience a DLT before completion of the last day of their DLT window, they will be considered as having completed their DLT window. Prior to opening a new cohort, the logistic regression model will be updated with the treatment outcome (i.e., the occurrence of DLT) and a new estimate of the MTD will be derived.

Enrollment into the next cohort will only resume after the Sponsor and the Investigators have jointly decided on the next dose-escalation step. Subject to clinical judgment, a new cohort of participants will be dosed at the new estimate of the MTD or the highest allowable dose based on pre-specified safety constraints as described below, whichever is lower and as guided by the mCRM-EWOC model. The design will continue as described, assigning participants to the MTD as estimated from all of the DLT data cumulatively, until one of the pre-defined stopping criteria is satisfied (see Section 4.1.4) or the pre-determined sample size of 60 DLT-evaluable participants is reached, whichever comes first. *Depending on emerging PK and safety data, the dose escalation may be evaluated taking into account sCEA levels at baseline in a sensitivity analysis (i.e. dose escalating more conservatively in the event toxicity is associated with low baseline sCEA levels).*

Built-in safety constraints are in place to prevent exposing participants to undue risk of toxicity, i.e., for Q3W dosing schedule, maximum allowable dose-increment, in absence of DLT, will be a maximum of 100%; if one DLT occurs then, an increment of 50% maximum will be allowed. The maximum dose that could be assessed in Part II will be 400 mg IV (see Section 4.3).

Provisional dose-levels in absence of DLT are listed in [Table 9](#).

Table 9 Provisional Dose Levels in Absence of DLT

Dose Level	Dose (mg)	Dose-Increment if no DLT (%)	Next Dose if no DLT (mg)
1	1.6	100	3.2
2	3.2	97	6.3
3	6.3	90	12
4	12	67	20
5	20	100	40
6	40	100	80
7	80	88	150
8	150	100	300
9	300	33	400
10	400	N/A	N/A

Dose-frequency may be adjusted depending on the emerging PK data for RO7172508 and given an appropriate previously observed safety and tolerability profile. Different dosing schedules (e.g., non-fractionated and/or fractionated dosing) may be tested in parallel. If a decision is made to adjust the dosing schedule during the course of dose-escalation, the mCRM-EWOC algorithm will be updated with the available participant data and adapted to account for any difference in exposure of the new schedule. The initial starting-dose will not exceed a dose already tested and considered safe. Safety and DLT window may also be adapted. If fractionated dosing is implemented, the DLT window will be extended until the end of the cycle in which the planned full dose is administered.

- Dose-escalation to SC MTD

Once an MTD or OBD has been defined, or relevant clinical activity is seen (e.g., PR or better according to RECIST) for IV route of administration and schedule, SC administration will be tested. The starting dose *and regimen* for SC will be proposed based on the evaluation of the safety and efficacy data observed following IV administration; however, due to practical considerations, a minimum dose of 2 mg is defined for a single SC administration (Section 4.3).

In the QW cohorts, RO7172508 will be administered *three times per cycle (i.e. QW)*, with a maximum starting-dose of one third of the RO7172508 IV MTD dose or, in case MTD has not been reached, of the highest safe dose ≥ 6 mg tested in the IV dose-escalation part. *For a Q3W regimen the starting dose will not exceed the highest safe dose tested in the IV Q3W dose escalation.*

The maximum allowed dose will be 160 mg QW *or* 400 mg Q3W (flat dose). Different dosing schedules (e.g., non-fractionated and/or fractionated dosing) may be tested.

For the SC administration, the mCRM-EWOC model will be updated to account for the available IV administration participant data and the difference in exposure with added uncertainty, given that the different routes of administration could lead to different safety profile. Each cohort will enroll a minimum of 3 participants. Enrollment and dose-escalation rules (i.e., stopping rules and maximum allowed increments) in Part II SC will be the same as the ones applied in Part II IV. DLT window will be the same as in Part II IV but may be updated based on emerging data. The dose-escalation will continue as described until one of the pre-defined stopping criteria is satisfied (see Section 4.1.4) or the pre-determined sample size of 60 DLT-evaluable participants is reached, whichever comes first.

No intra-participant dose-escalation will be allowed in Part II.

The OBD (IV and SC) will be selected based on the overall clinical safety and activity, as well as available PK and PD data for RO7172508. *Data will be listed and summarized by dose group as described in the analysis section (see Section 9.4).*

Once a schedule, route of administration and OBD has been selected, and in case efficacy is observed during dose-escalation, disease-specific expansions may be opened to confirm these efficacy signals. The protocol will be amended in this case to describe treatment of these cohorts. *If one route of administration is not unequivocally superior, and a decision cannot be taken during or at the end of dose escalation, both routes of administration may be compared in disease specific expansions. Criteria for selection of a route of administration will then be added via the protocol amendment preceding the expansions, including endpoints.*

4.1.3 Obinutuzumab Pre-treatment

[figure not shown]
During the course of the study, the need for obinutuzumab pre-treatment will be assessed based on loss of RO7172508 exposure and/or ADA-related safety events. Previous experience with the combination of immunotherapy and obinutuzumab has shown the capacity of obinutuzumab to abrogate ADA formation, thereby maintaining exposure to the investigational compound as determined by PK analysis (see Section 2.2.2 and the RO7172508 investigator's brochure for further references).

During the course of the dose escalation, the decision to implement obinutuzumab will be based on a Bayesian posterior probability approach (see [Appendix 8](#) for further details). At the time of the evaluation, if there is high confidence (80% confidence level) that the underlying true rate of participants with relevant loss of exposure is above 50% then obinutuzumab pre-treatment will be introduced for all subsequent participants in the study (see Section 6.1 and [Appendix 8](#)). If the criteria are not met, the dose escalation will proceed without obinutuzumab pre-treatment until the next assessment or the end of the dose escalation, whichever is reached first (see [Appendix 8](#)).

If obinutuzumab will be implemented during the course of the dose escalation, then the dose escalation will be run under the same condition as defined for Part II without obinutuzumab. The starting dose will be a dose that has been safely tolerated in Part II without obinutuzumab. Escalation, stopping rules and maximum number of participants applied to Part II will also apply to Part II with obinutuzumab pre-treatment.

The first assessment on the implementation of obinutuzumab will be conducted once PK data following 3 cycles of treatment are available from at least 14 participants across both Part I and II (see [Appendix 8](#)). Loss of exposure is defined as at least a 70% reduction in C_{max} at Cycle 3 from Cycle 1 in a participant. This threshold may be adapted based on emerging PK data. Ongoing assessments of safety and PK data will be performed for each cohort and at the end of dose escalation, to continuously evaluate the criteria for implementation of obinutuzumab pre-treatment. In addition, the incidence and titer of ADAs will be assessed on an ongoing basis throughout the study.

[figure not shown]
Figure 4 *Decision Tree During Dose Escalation*

If at the end of the dose escalation, the criteria to implement obinutuzumab pretreatment has not been met and at the same time, there is low confidence (i.e. <70% confidence level) that the true rate of loss of exposure is < 5%, then additional participants will be enrolled (see [Appendix 8](#)). Participants will then be randomized to cohorts at the OBD with or without obinutuzumab to further evaluate the safety and PK profile.

The need of obinutuzumab for further clinical development of RO7172508 will be determined based on the overall assessment of safety and PK data as well as pharmacodynamics effects.

Figure 5 *Decision Tree at End of Dose Escalation*

The total number of participants with relevant loss of exposure required to meet the criteria at subsequent evaluations, will depend on the actual number of participants enrolled and on the number of cohorts necessary to complete the dose escalation. For operating characteristics see [Appendix 8](#).

Independent from loss of exposure, obinutuzumab pretreatment will be initiated if there is evidence of ADA-mediated hypersensitivity reactions or other safety signals that are likely related to ADAs. In such instance, obinutuzumab will be implemented for all subsequent participants and the enrollment of participants without obinutuzumab will be stopped.

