Tumor Assessment ^k	X							X ^k				X ^k			X			
sCEA	X	X	X	X	X	X	X	X	X	X	X	X	X		X	X		X
RO7172508 PK Sample		X	X	X	X	X	X	X	X	X	X	X	X	X	X	X		X
ADA to RO7172508		X					X	X	X		X	X	X		X	X		X
PD Blood Cytokines		X	X	X	X	X	X	X	X	X		X ⁿ	X ^r	X ⁿ	X			X ^p
IgE and Tryptase																		X ^p

Notes: ADA=anti-drug antibody; AE=adverse event; C=Cycle; CEA=carcinoembryonic antigen; D=day; discontin=discontinuation; ECG=electrocardiogram; ECOG=Eastern Cooperative Oncology Group; G2=grade 2; HIV=human immunodeficiency virus; IgE=immunoglobulin E; incl=including; IRR=infusion related reaction; PD=pharmacodynamics; PK=pharmacokinetic; RECIST=Response Evaluation Criteria in Solid Tumors; sCEA=soluble CEA.

- All visits from Cycle 3 onwards should occur within a 3-day time window, unless otherwise indicated and all assessments or samples where indicated should be taken prior to the administration of RO7172508.
- Informed consent must be obtained before any study-specific procedures *and may be obtained > 28 days before the start of study treatment*.
- Physical examinations to be performed on days of treatment administration, and at the 60-day safety follow-up.
- Weight to be recorded pre-infusion. Height to be measured at screening only.

Table 1 Part I: Single Participant Cohorts IV/Multiple-ascending Dose-escalation (cont.)

- e) 12-lead ECG at screening (within one week before first dose of RO7172508). After Cycle 5, 12-lead ECG to be done only at every second cycle (i.e., C7, C9 etc.). Additional unscheduled triplicate ECG assessments should be performed in case of abnormalities and/or if clinical symptoms occur. Recording must be done prior to PK sampling.
- f) Serum pregnancy test at screening, within 7 days prior to first dose, and at the safety follow-up visit; a urine pregnancy test will be performed at specified subsequent visits. If a urine pregnancy test is positive, it must be confirmed by a blood pregnancy test. Results must be obtained and reviewed prior to administration of RO7172508.
- g) All planned assessments are to be performed before administration of RO7172508. All participants in Part I of the study will receive, as a minimum, one dose of RO7172508. If there are no safety concerns, participants may receive further doses Q3W at the same dose level. Dose escalation for individual participants to the next available tolerated dose level can only proceed after a participant has tolerated their current dose for at least two cycles.

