During the course of this study, the need for obinutuzumab pretreatment will be assessed based on loss of RO7172508 exposure and/or ADA-related safety events. Details, including decision criteria, are provided in Section 4.1.3 and Appendix 9. If on-target toxicity is reported predominantly in the first cycle of treatment, fractionated dosing may be implemented for the first cycle to improve tolerability. RO7172508 treatment would start with 10% of the planned dose on Cycle 1 Day 1, 30% of the planned dose on Cycle 1 Day 8 and 60% of the planned target dose on Cycle 1 Day 15, followed by the full dose treatment from Cycle 2 Day 1 onwards as described in Figure 2. By using a step-up fractionated dosing approach, it is predicted that the lower peak exposures (C_{max}) will result in lower cytokine levels to that when the full dose is given on Day 1. The fractionated dosing regimen may be adjusted depending on emerging data and in discussion with the Investigators. A similar approach to increase the dose administered during the first three weeks as applied with dose-fractionation in the Q3W treatment group, may also be employed in the once weekly (QW) treatment group. If a patient in the fractionated dose cohort experiences any adverse event that results in a delay of the next administration of RO7172508 beyond one week, the dose at which the treatment should be restarted will require agreement between the investigator and the Sponsor.

Figure 2 Fractionated Dosing Design for Q3W and QW

At least 3 evaluable participants will be treated in each cohort during the IV or SC dose-escalation regimen.

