4.1.2 Dose-Escalation Decision Criteria

4.1.2.1 Part I: Multiple-Ascending Dose-Escalation (Single Participant Cohorts)

[figure not shown]
In Part I, RO7172508 will be administered IV Q3W with a flat dose. The starting-dose of RO7172508 will be 65 µg (see Section 4.3 for starting dose justification) and the maximum dose explored will be 1.6 mg. An increment-based escalation will be utilized. The first 2-step increments (up to 400 µg) are 2.5 as the first doses are considered low and sub-therapeutic. From 400 µg dose, a maximum of 3-fold increments will apply (see Section 4.3).

Thus, the 65 µg starting-dose is followed by doses of 160 µg, 400 µg, 800 µg and 1600 µg. Incremental dose-increases may be altered based on emerging PK, PD and safety data but will not exceed 3-fold.

Each cohort will include one participant in order to minimize the number of participants treated below the predicted therapeutically relevant dose. Each participant will be followed up for a 4-week dose limiting toxicity (DLT) window (Figure 3). The DLT window is divided into a 14-day safety observation period, after which the next cohort could be opened, and a further observation period of two weeks, to assess any potential late toxicity including up to one week after the second administration (i.e., total of 4 weeks).

Enrollment into the subsequent cohort will occur after the Sponsor and the Investigators have jointly decided on the next dose-escalation step. A telephone conference will be held with Investigators before a new dose-level is opened, where all available safety, PK and PD data will be evaluated. The next cohort will open if no RO7172508-related AE of Grade ≥ 2 (or DLT) is reported in a participant during the 14-day safety observation period. If a related Grade ≥ 2 AE or DLT occurs after the 14-day safety window and within the 4 weeks DLT window in a lower dose cohort, then participants at a higher dose may have their dose reduced for subsequent cycles and the switch from Part I to Part II of the study is triggered.

Figure 3 Part I: Observation and DLT Windows

Intra-participant dose-escalation is allowed in Part I. A participant (e.g., Cohort 1/Participant 1) can progressively escalate to a dose-level tolerated by subsequent cohorts if:

- Participant has completed his/her current cohort's 4-week DLT window and experienced no RO7172508-related Grade ≥ 2 AEs.

AND

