- Participant in the next highest level cohort (i.e., Cohort 2/Participant 2) has safely passed his/her 14-day safety observation window.

The maximum dose-level allowed for participants in Part I will be the highest dose-level administered in Part I. Participants may continue to receive RO7172508 for up to 24 months, until disease progression, or loss of benefit (see Section 7).

Participants who undergo dose-escalation will not need to complete another 4-week DLT assessment period. All other rules for subsequent escalations still apply as noted above.

The Sponsor will switch from Part I to Part II when either a dose of 1.6 mg IV (flat dose) is reached or the occurrence of a RO7172508-related Grade ≥ 2 AE (or DLT) is observed, whichever comes first. The Sponsor may decide to switch from Part I to Part II in the absence of an observed RO7172508-related Grade ≥ 2 toxicity or prior to the dose-level reaching 1.6 mg.

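### The loss-of-exposure rule compares Cmax at Cycle 3 with Cycle 1 without regard to dose, so participants whose dose differs between those cycles face a different threshold in the count that triggers obinutuzumab

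*Combined protocol and SAP*

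**What the plan says.** Section 4.1.3 bases the decision to introduce obinutuzumab during escalation on the number of participants with loss of exposure: "Loss of exposure is defined as at least a 70% reduction in C_{max} at Cycle 3 from Cycle 1 in a participant". The one flexibility attached to the definition is "This threshold may be adapted based on emerging PK data". The first assessment pools Part I and Part II and needs Cycle 3 PK data from at least 14 participants. Appendix 8 section 2.2 repeats the assessment after each cohort. If the posterior probability that the true rate is at least 50% exceeds 80%, all subsequent participants receive obinutuzumab; Appendix 8 section 2.3 translates this into 9 of 14 at the first look and 24 of 41 at the last.

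Elsewhere the protocol lets the dose differ between Cycles 1 and 3:

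- **Part I escalation.** Table 1, footnote g, says that individual escalation "can only proceed after a participant has tolerated their current dose for at least two cycles", so the earliest higher dose is at Cycle 3, the cycle the rule reads. Section 4.1.2.1 caps it: "The maximum dose-level allowed for participants in Part I will be the highest dose-level administered in Part I". Section 4.1.2.2 rules it out later: "No intra-participant dose-escalation will be allowed in Part II".
- **Optional fractionated Cycle 1.** Section 4.1 gives 10% on Day 1, then "30% of the planned dose on Cycle 1 Day 8 and 60% of the planned target dose on Cycle 1 Day 15", then the full dose from Cycle 2.
- **Dose reduction.** In Part I, "participants at a higher dose may have their dose reduced for subsequent cycles". Section 6.6 also permits reduction after a DLT or a recurrent toxicity.

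Section 9.4.4 lists no dose-normalised PK parameter. Appendix 8 counts evaluable participants without saying whether those with a changed dose are included.

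**The concern.** Cmax depends on dose as well as on immunogenicity. If the dose rises between Cycles 1 and 3, a real loss is partly hidden; if it falls, a smaller loss crosses the 70% line. Two participants with the same proportional loss can therefore be counted differently because of their dose history. The count drives a rule that binds everyone enrolled afterwards, so a misclassified participant can delay or hasten a change of regimen for the rest of the study.

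There is also an ambiguity of reference. A fractionated Cycle 1 has three peaks, and the SC QW schedule (three administrations per cycle, Section 4.1.2.2) has the same structure. The rule does not say which peak is meant.

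**Working it through.** **Reproducing the plan's figures.** The prior is Beta(0.6667, 0.3333), the target 50% and the threshold 80% (Appendix 8 sections 2.1 to 2.3). With x losses among n, the posterior is Beta(0.6667 + x, 0.3333 + n − x).

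- P(rate > 0.5) is 0.877 at 9/14 and 0.733 at 8/14; it is 0.874 at 24/41 and 0.797 at 23/41. Both stated cut-offs reproduce.
- Cut-offs at n = 14, 17, 20, …, 41 are 9, 11, 12, 14, 15, 17, 19, 20, 22, 24.
- Exact trigger probabilities (first look / all ten looks) are 48.6% / 82.0% at a true rate of 60% (stated 48.65% / 81.81%) and 5.8% / 10.8% at 40% (stated 5.74% / 11.06%).

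The arithmetic of Appendix 8 is sound. The question is what enters it.

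**Loss needed to register.** Let D be the Cycle 3 dose divided by the dose behind the Cycle 1 reference peak. With dose-proportional Cmax and no accumulation, the rule flags when D × (1 − loss) ≤ 0.30, so the dose-normalised loss needed is 1 − 0.30/D.

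| Situation | D | Loss needed |
|---|---|---|
| Unchanged dose | 1 | 70% |
| Part I step 400 to 800 µg, or 800 to 1600 µg | 2 | 85% |
| Part I step 160 to 400 µg | 2.5 | 88% |
| Fractionated, Day 15 reference | 1/0.6 = 1.67 | 82% |
| Dose cut by one third (assumed) | 2/3 | 55% |
| Dose halved (assumed) | 1/2 | 40% |

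Setting the loss to zero gives D ≤ 0.30: a participant with no loss is flagged only if the dose is cut to 30% or less.

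**Carry-over for the fractionated case.** The documents give no half-life, so 3 to 14 days is assumed in a one-compartment model, with e(d) = exp(−d·ln2/half-life). The Day 15 peak is 0.6 + 0.3e(7) + 0.1e(14). The no-loss Cycle 3 peak is 1 + e(21) + 0.6e(28) + 0.3e(35) + 0.1e(42). At 7 days these are 0.775 and 1.173, so the loss needed is 1 − 0.30 × 0.775/1.173 = 80.2%. Over 3 to 14 days it is 80% to 84%. At an unchanged dose the same model gives 1 − 0.30/(1 + e(21) + e(42)) = 70% to 80%.

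**Effect on the trigger.** Part I has about 5 single-participant cohorts and the last is already at the top dose, so at most about 5 − 1 = 4 can escalate. Let k of the first 14 be escalators whose losses register with probability r. The first-look count is Bin(14 − k, 0.6) + Bin(k, 0.6r), and each later look adds Bin(3, 0.6).

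| k | r | First look | All looks |
|---|---|---|---|
| 0 | – | 48.6% | 82.0% |
| 2 | 0.5 | 35.4% | 74.9% |
| 4 | 0 (extreme bound) | 4.6% | 48.0% |

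The documents give neither k nor r.

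**Backstop.** At the end of escalation the randomised comparison is skipped only if the posterior probability of a rate below 5% reaches 70%. That probability is 0.711 at 1/41 and 0.423 at 2/41, so skipping requires at most 1 counted loss of 41. Even with 4 escalators who never register, this has probability 0.3% at a true rate of 20%.

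**The case against.** The strongest reply is that few people are affected and the protocol has other safeguards. Much of this stands. Part II participants on an unchanged, non-fractionated dose have no mismatch. Fractionation is optional. Four escalators would require nearly every Part I participant to reach Cycle 3 without a related Grade ≥ 2 event in the DLT window and then actually be escalated. The assumption that their losses never register leaves out complete loss of exposure, which the raw rule does catch. If the trigger is missed, "Participants will then be randomized to cohorts at the OBD with or without obinutuzumab" still follows unless almost no losses are counted, and obinutuzumab starts independently on an ADA-related safety signal.

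It can also be said that the threshold may be adapted. For fractionation that could work, because the dose ratio is fixed by the regimen. It cannot repair ratios that vary between participants, as they do for Part I escalators and reduced doses. The PK population in Section 9.3 excludes incomplete data and significant protocol deviations; an escalation or reduction made according to protocol is neither.

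Three stronger readings are tempting and are not supported:

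- **That a fractionated participant needs a loss of 91% or 97%.** These figures use the 30% and 10% peaks as reference. Cmax is the maximum concentration, so the natural reading for Cycle 1 is the highest peak, the one on Day 15.
- **That reduced-dose participants would register as losses regardless.** A halved dose with no loss shows a fall of about 50% and is not flagged. A reduction lowers the bar but does not by itself create events, unless the dose falls to 30% or less.
- **That the stated operating characteristics are wrong.** They reproduce; they describe counted events.

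**Conclusion.** The point holds and should be fixed before the first assessment. As written, the rule applies a different effective threshold to anyone whose dose differs between Cycles 1 and 3: higher for escalators (85% to 88%) and for a fractionated Cycle 1 (about 82%, or 80% to 84% with carry-over), and lower after a dose reduction (40% to 55% for the assumed cuts). The practical consequence is a trigger that comes late or early, not the loss of the obinutuzumab question altogether. A moderate illustration is a fall in the all-look trigger chance from 82.0% to 74.9%; 48.0% is an extreme bound.

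The absence of a dose term is certain from the text. The magnitudes rest on dose-proportional Cmax, an assumed half-life, assumed cut sizes, and assumed values of k and r.

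A separate inconsistency concerns what is counted. Section 4.1.3 and the 9/14 and 24/41 statements count any loss of exposure. Section 4.3.2, the opening of Appendix 8 section 2, section 2.1 and the 1/41 statement in section 2.3 tie the loss to ADAs. These passages must be reconciled; this review does not choose between them.

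**What to change.** In Section 4.1.3 and Appendix 8 section 2.2:

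1. Define loss of exposure as a fall of at least 70% from Cycle 1 to Cycle 3 in Cmax divided by the dose given at that administration.
2. Where Cycle 1 has several administrations (fractionated IV, SC QW), state that the reference is the peak after the last Cycle 1 dose divided by that dose, compared with the matching Cycle 3 peak.
3. At each look, report a sensitivity count that excludes participants whose dose changed. This needs no assumption of dose proportionality.
4. Separately, state once whether the counted event is any loss of exposure or loss due to ADAs, and align the passages.

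The cost is wording and one extra count per look. Dose and PK data are already collected, and Table 4 schedules an end-of-infusion PK sample on Cycle 1 Day 15. The posterior rule and its cut-offs stay as they are, and no dose is altered. Two limits remain: the primary count assumes dose-proportional Cmax, and dividing by dose does not remove accumulation, so under the assumed half-lives a participant on an unchanged dose still needs a loss of 70% to 80%.
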